## 7.4 ADVERSE EXPERIENCE REPORTING

To assure the safety of the subjects, information about all AEs (see [Section 7.1](#)), whether volunteered by the subject, discovered by investigator or study staff questioning, or detected through physical examination, laboratory test or other means, will be collected and recorded in the subject's source documents and followed as appropriate.

### 7.4.1 TRIAL REPORTING PERIOD OF ADVERSE EVENTS

All solicited and unsolicited adverse events will be collected throughout the study and recorded in the electronic data capture (EDC) system.

### 7.4.2 TRIAL REPORTING PERIOD OF SERIOUS ADVERSE EVENTS

The reporting period for SAEs (without regard to causality or relationship) is comprised of the period following the signing of the informed consent form until the end of the study. Each AE will be assessed to determine whether it meets seriousness criteria. If the AE is considered serious, the investigator should record this event in the EDC system and report the event to the Sponsor within 24 hours of becoming aware of the event. The investigator may also directly report this event to the Ethics Committee according to its standard operating procedures. Expectedness of SAEs will be determined by the Sponsor using reference safety information specified in the Investigator's Brochure and protocol.

An event may qualify for expedited reporting to regulatory authorities if it is an SAE, unexpected per reference safety information and considered related following the guidelines in [Section 7.1.6](#) (Suspected Unexpected Serious Adverse Reaction, SUSAR) and [7.1.7](#) (Unanticipated [serious] adverse device effect) in line with relevant legislation. All investigators will receive a safety letter notifying them of relevant SUSAR reports. The investigator should notify the Institutional Review Board (IRB)/Ethics Committee (EC) as soon as is practical, of serious events in writing where this is required by local regulatory authorities, and in accordance with the local institutional policy.

At any time after completion of the SAE reporting period, if an investigator becomes aware of an SAE that is suspected by the investigator to be related to the study drug, the event will be reported to the Sponsor or its designee. If the investigator becomes aware of an SAE in a study subject after the last scheduled follow-up visit, and considers the event related to prior Study Treatment, the investigator will report it to the Sponsor or the appropriate designee.

#### 7.4.3 NOTIFICATION OF SERIOUS ADVERSE EVENTS

In accordance with local regulations, the Sponsor shall notify the appropriate regulatory authorities, and all participating investigators in a written safety report of any adverse experience associated with the use of the product that is both serious and unexpected and any significant new safety information that might materially influence the benefit-risk assessment of a medicinal product, sufficient to consider changes in product administration or overall conduct of a clinical investigation. The Sponsor will notify regulatory agencies within the time frame specified by local requirements but no later than 10 working days for UADE, 7 days for a fatal or life-threatening SUSAR and 15 days for all other SUSARS (see [Section 7.1.6](#) and [7.1.7](#)).

#### 7.4.4 REPORTING OF DEVICE RELATED COMPLAINTS

A product complaint (or device deficiency) involves any written, electronic, or oral communication that alleges deficiencies related to the identity, quality, durability, reliability, safety, effectiveness, or performance of a device such as malfunction, misuse or use error and inadequate labeling. A malfunction is defined as the failure of a device to meet its performance specifications or otherwise perform as intended. The intended performance of a device refers to the intended use for which the device is labeled. All product complaints that meet this definition must be reported to the sponsor within 10 days of discovery. Any product complaint that involves an AE or SAE must be also be reported per [Section 7.4.1](#) and [Section 7.4.2](#).

Any problems experienced including potential malfunctions of the device, error messages displayed on the device screen following treatment or errors that occur during the treatment procedure must be reported to the Sponsor or designee immediately for evaluation.

Additional instructions on complaint reporting to be provided separately.

## 7.5 TRIAL DISCONTINUATION

Inovio Pharmaceuticals reserves the right to discontinue the study at this site or at multiple sites for safety or administrative reasons at any time. In particular, a site that does not recruit at a reasonable rate may be discontinued. Should the study be terminated and/or the site closed for whatever reason, all non-source documentation and study product pertaining to the study must be returned to Inovio Pharmaceuticals or its representative.

The study may be discontinued at any time by an IRB, Inovio Pharmaceuticals Inc., the FDA or other government agencies as part of their duties to ensure that research subjects are protected.

## 8. STATISTICAL ANALYSIS PLAN

### 8.1 GENERAL CONSIDERATIONS

The statistical analysis of the data will be performed by Inovio Pharmaceuticals or its representative.

This is a two-arm, multi-center, open-label randomized clinical trial of VGX-3100 and VGX-3100 with imiquimod, in subjects with a histologic diagnosis vulvar HSIL and confirmed vulvar infection with HPV types 16 and/or 18. The study's primary endpoint is binary: regression of vulvar HSIL and viral clearance of HPV-16 and/or HPV-18 from vulvar tissue based on tissue collected at Week 48. The primary hypothesis is that each of the treatment arms will result in regression of HSIL and clearance. Secondary efficacy analyses pertain to regression, clearance of HPV-16 and/or HPV-18 infection, regression to normal, non-progression, and anatomic extent. Other secondary analyses concern safety and humoral and cellular immunological measures. Exploratory efficacy analyses concern extended dosing with respect to regression, clearance, and anatomic extent, clearance outside of the vulva, and effect of HLA type on efficacy. Other exploratory analyses pertain to tissue immunological measures, effect of needle depth into muscle on efficacy, and patient-reported outcomes.

### 8.2 RANDOMIZATION AND BLINDING

Subjects will be randomized two to one, VGX-3100 alone: VGX-3100 in combination with topical imiquimod. Subjects will be randomized in a stratified manner according to (a) recurrent disease at screening (0 vs. 1 or more recurrences), (b) multifocal disease (1 vs. 2 or more lesions at screening), (c) Body Mass Index (BMI) category ( $\leq 25$  vs.  $> 25$  kg/m^2), and (d) age category ( $< 45$  years vs.  $\geq 45$  years). There are no requirements for the number of subjects in each stratum. The study is open-label.

### 8.3 SAMPLE SIZE/POWER

A sample of 36 subjects will be randomized to receive either 6 mg VGX-3100 or 6 mg VGX-3100 plus imiquimod, IM followed by EP in a 2:1 ratio. This sample size provides 80% power to declare each arm superior to historical control, assuming the true proportion of subjects who achieve the primary endpoint is 20% and 28% for the respective treatment arms and 2% for the historical control, and that 90% are evaluable at Week 48 from randomization.

## 8.4 ANALYSES POPULATIONS

Analysis populations will include:

- The modified intention to treat (mITT) population includes all subjects who receive at least one dose of Study Treatment and who have the analysis endpoint of interest. Subjects in this sample will be grouped to treatment arms as randomized. Analysis of the mITT population will be primary for the analysis of efficacy in this study.
- The per-protocol (PP) population comprises subjects who receive all doses of Study Treatments and have no protocol violations and who have the analysis endpoint of interest. Subjects in this sample will be grouped to treatment arms as randomized. Analyses on the PP population will be considered supportive of the corresponding mITT population for the analysis of efficacy. Subjects excluded from the PP population will be identified and documented prior to unblinding of the study database.
- The safety analysis set includes all subjects who receive at least one does of Study Treatment. Subjects will be analyzed as to the treatment they received.

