## 8.9 EFFICACY ANALYSIS

The true treatment effect on the primary endpoint is  $p$ , where  $p$  denotes the true population probability of the primary endpoint for each arm. The primary hypothesis of superiority is:  $H_0: p \leq 0.02$  vs.  $H_1: p > 0.02$ , for each treatment arm separately.

A p-value for these hypothesis tests and corresponding 95% confidence intervals will be computed based on the method of Clopper-Pearson. Superiority will be concluded if the one-sided p-value is  $< 0.025$  and the corresponding lower bound of the 95% CI exceeds 0.02.

The secondary efficacy binary endpoints will be analyzed in the same manner as the primary hypothesis, but without the hypothesis test p-values.

For the analyses, the efficacy time frame is defined by any time starting from 14 days prior to the -specified visit week.

The anatomic extent endpoint will be analyzed by calculating the mean percent change and associated 95% t-distribution based confidence interval. The percentage of subjects with no clinically significant lesion resolution (reduction in lesion size of 25% or less), partial lesion resolution (26-99% reduction), and complete reduction (100% reduction) will be summarized with point estimates and associated Clopper-Pearson 95% confidence intervals.

An exploratory analysis will examine clearance outside of the vulva. This will be analyzed in the same manner as vulvar clearance.

An exploratory analysis will examine the relationship between the primary efficacy endpoint and HLA results. As these results are categorical, relationships will be examined with contingency tables and logistic regression models which model the primary endpoint versus these results and treatment group as regressor variables.

An exploratory analysis will examine the relationship between the primary efficacy endpoint and needle depth into muscle. A logistic regression model which models the primary endpoint versus these results and treatment group as regressor variables will be used.

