#### 8.11.6 MISSING VALUES

Missing data will not be imputed or replaced, and calculations will be done on reported values.

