The decision process following results of the Week 74 biopsy are described in [Figure 3](#) and are as follows: At Week 74, the subject will undergo repeat vulvar punch biopsy/biopsies of the same lesion as study start, but adjacent to the original site within the boundaries of the original lesion (see [Table 3](#)). If after evaluation of biopsy tissue by the PAC there is no evidence of HSIL (Subgroups A or B), the subject will continue to Week 96 for vulvoscopy, and biopsy adjacent to the site of the initial biopsy.

If HSIL remains but there is a reduction in lesion size or no increase in lesion size from baseline (Subgroups C or D), the Investigator has the option to give the subject a 6th dose of VGX-3100 at Week 78, and the subject will continue on study with vulvoscopy and

biopsy at Week 96. Alternatively, the Investigator may choose to treat the subject with surgical or standard treatment, and the subject will continue on study without further biopsy.

The decision process following results of the Week 74 biopsy are as described in [Figure 4](#) and are as follows: At Week 96, the subject will undergo repeat vulvar punch biopsy/biopsies of the same lesion as study start, but adjacent to the original site within the boundaries of the original lesion (see [Table 3](#)). If there is no vulvar HSIL (Subgroups A or B), no further procedures are required. If after evaluation of biopsy tissue by the PAC there is vulvar HSIL (Subgroups C or D), or worsening disease (Subgroup E), the subject will receive surgical or other standard treatment.

In the event of worsening disease (ie, Subgroup E - any increase in lesion area from baseline or worsening of HSIL to cancer), the subject will receive surgical treatment per the Investigator's judgement and will continue on study through Week 100 with vulvoscopy, but without further biopsy. For a finding of carcinoma, subjects will receive surgical treatment, and be discontinued from study treatment. The event will be reported as an SAE per [section 7.1.4](#). If wide excision is required, the sample obtained will be sent to the PAC for evaluation.

Pre-biopsy Vulvoscopy Finding	Minimally required procedure
No acetowhite lesion	Vulvar punch biopsy and imaging; biopsy should be conducted of the same lesion as study entry, but adjacent to the original biopsy site within the boundaries of the original lesion;

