#### 4.3.2 CRITERIA FOR WITHDRAWAL FROM THE STUDY

All subjects who begin treatment should be encouraged to complete all phases of the study, including those who discontinue treatment. A subject may voluntarily withdraw from study participation at any time. A subject may be withdrawn at any time at the discretion of the investigator for any maternal obstetrical or medical complications after consultation with the medical monitor.

Subjects who become ineligible to continue on study based on no longer meeting exclusion criteria should be discontinued from study treatment, managed per routine standard of care and should continue on study without further biopsy.

Subjects who are withdrawn from study participation after starting treatment will not be replaced. Reasons for study withdrawal will be recorded in the electronic case report form (eCRF) and the subject's source document

Should a subject fail to attend the clinic for a required study visit, the site should attempt to contact the subject and reschedule the missed visit as soon as possible. The site should also counsel the subject on the importance of maintaining the assigned visit schedule for follow-up and treatment of VIN, and ascertain whether or not the subject wishes to and/or should continue in the study based on previous noncompliance. In cases where the subject does not return for the rescheduled visit or cannot be reached to reschedule the missed visit, the site should make every effort to regain contact with the subject (3 telephone calls to the subject should be made and if that fails, then a certified letter is sent to the subject's last known mailing address) so that they can be considered withdrawn from the study for disposition purposes. These contact attempts should be documented in the subject's medical record. Should the subject continue to be unreachable, then and only then will she be considered to have withdrawn from the study with a primary reason of "Lost to Follow-up." For all other subjects withdrawing from the study, an alternative reason for discontinuation should be recorded in the eCRF.

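### The primary efficacy set drops dosed women without a Week 48 result instead of counting them as non-responders, which biases the response rate and its interval upward, though hardly the superiority decision

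*Protocol*

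**What the plan says.** Protocol section 8.4 defines the mITT population as one that "includes all subjects who receive at least one dose of Study Treatment and who have the analysis endpoint of interest", and adds: "Analysis of the mITT population will be primary for the analysis of efficacy in this study". The supportive per-protocol set carries the same endpoint condition. Section 8.11.6 states: "Missing data will not be imputed or replaced, and calculations will be done on reported values". No efficacy analysis of all dosed subjects is described.

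Several other passages decide who will have the endpoint:

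- **Section 3.2, worsening disease (any increase in lesion area, or cancer).** The woman receives surgery at the investigator's judgement and "will continue on study through Week 100 with vulvoscopy, but without further biopsy". The synopsis version adds that this applies at any time. Both versions send tissue from a wide excision to the Pathology Adjudication Committee (PAC).
- **Section 4.3.2.** Subjects who become ineligible stop study treatment and "should continue on study without further biopsy". Subjects withdrawn after starting treatment are not replaced.
- **Section 3.2.1, Table 4.** Non-responders are women with HSIL, AIS, carcinoma or HPV-16/18 at evaluation, and women given non-study medication for VIN. Surgery, lesion growth without carcinoma, dropout and missing results are not named.
- **Section 8.9.** The efficacy time frame opens 14 days before the visit week. Each arm is tested separately, and success requires a one-sided p below 0.025 with the "lower bound of the 95% CI exceeds 0.02".

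Section 8 can be read in protocol versions 1.0 and 1.1. The version 1.2 text at hand ends before it. The version 1.2 summary of changes names only the removal of one questionnaire and calls its other changes administrative.

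**The concern.** Whether a woman has a Week 48 tissue result can depend on how she is doing. A woman operated on at Week 27 for a growing lesion has not responded in any ordinary sense. Her tissue predates the 8.9 window, she is not biopsied again, and Table 4 does not name surgery. Read literally, section 8.4 removes her rather than counting her as a failure.

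Each arm is judged against a constant, so no concurrent control loses subjects in the same way. The reported figure becomes the response rate among women who reached an evaluable biopsy, whereas the hypothesis in section 2 concerns the women treated. In a pilot study of 36 subjects, the response rate and its interval are main results.

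**Working it through.** **Inputs.** Arms of 24 and 12 (section 3). Null rate 2% and exact one-sided test at 0.025 (8.9). Section 8.3 assumes "the true proportion of subjects who achieve the primary endpoint is 20% and 28% for the respective treatment arms and 2% for the historical control", with 90% evaluable at Week 48.

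**1. The plan's own power.** Evaluable numbers are 24 × 0.9 = 21.6 and 12 × 0.9 = 10.8, rounded down to 21 and 10. The critical count r is the smallest with P(X ≥ r | n, 0.02) < 0.025.

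| Arm | n | r | Exact alpha | Power |
|---|---|---|---|---|
| VGX-3100 (20%) | 21 | 3 | 0.0081 | 82.1% |
| With imiquimod (28%) | 10 | 2 | 0.0162 | 81.7% |

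The stated 80% is reproduced as a lower bound in both arms.

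**2. Inflation.** If a share d of dosed subjects is dropped and all of them are failures, the reported rate is p/(1 − d).

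- d = 10% (the protocol's figure): 1/0.9 = 1.11. Taking 20% and 28% as rates among evaluable subjects, the all-dosed rates are 0.20 × 0.9 = 18.0% and 0.28 × 0.9 = 25.2%.
- d = 20% (assumed): 1/0.8 = 1.25.
- d = 30% (assumed): 1/0.7 = 1.43.

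Illustrations:

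- 4 responders with 4 of 24 missing: 4/20 = 20.0% (95% CI 5.7–43.7) against 4/24 = 16.7% (4.7–37.4).
- 5 responders with 6 of 24 missing: 5/18 = 27.8% (9.7–53.5) against 5/24 = 20.8% (7.1–42.2).
- 3 responders with 3 of 12 missing: 3/9 = 33.3% against 3/12 = 25.0%.

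**3. The superiority decision.** The critical count is 3 for every n from 13 to 24, and 2 for 6 to 12. Removing failures therefore does not change the number of responders needed unless about half of the larger arm is missing. At that point 2/12 gives p = 0.023 and passes, while 2/24 gives p = 0.083 and does not.

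**4. Power with all dosed subjects in the denominator.** Critical counts are 3/24 (alpha 0.0118) and 2/12 (alpha 0.0231). With 20% and 28% as rates among evaluable subjects and missing counted as failure:

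| Missing | Rates | Power, n = 24 | Power, n = 12 |
|---|---|---|---|
| 10% | 18.0%, 25.2% | 83.3% | 84.5% |
| 20% | 16.0%, 22.4% | 76.3% | 78.7% |
| 30% | 14.0%, 19.6% | 67.3% | 71.4% |

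**The case against.** The strongest reply is that the protocol does count many of these women.

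- **Failures already named.** Table 4 names HSIL, AIS, carcinoma and HPV-16/18 at evaluation, without tying evaluation to Week 48, and it also names non-study medication. The primary endpoint accepts excised tissue, and a wide excision goes to the PAC. This stands in part. A reader might infer that every woman who worsens disappears from the analysis, and the documents do not support that. What they show is that Table 4, the excision sentence, the 8.9 window and 8.4 are not reconciled for surgery before about Week 46.
- **A narrow exit path.** Surgery is at the investigator's judgement. Table 13 lets women whose unscheduled biopsy shows HSIL continue on schedule. The 8.9 window has no stated end, so a late biopsy can count. This limits how many women are affected but does not close the gap.
- **Missing is not the same as failure.** A subject may become ineligible or drop out for reasons unrelated to response. This is fair: failure is likely for women operated on for growth and an assumption for the others.
- **A planned loss of 10%.** Nothing in the protocol supports 20–30%, so the 1.11-fold figure leads.
- **A pilot study with disposition reported by reason.** Readers could recompute an all-dosed rate, and sensitivity analyses are often left to the SAP. However, the primary set and the imputation rule are fixed here, and both point the same way.

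**Conclusion.** The point holds as a bias in the estimate and confidence interval. It is 1.11-fold at the planned 10% non-evaluable if all of those women are failures, and 1.25- to 1.43-fold at an assumed 20–30%. If some of the missing women would have responded, the bias is smaller.

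A reader might infer that the trial could claim superiority because failures were removed. The exact test does not support that: the responder counts needed stay the same unless about half of the 24-subject arm lacks the endpoint. Nor is it right that counting missing as failure never costs power. The 80% holds at the planned 10% missing, but at 20% or more it does not if 20% and 28% are rates among evaluable subjects.

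The matter should be fixed. It is not fatal to the design.

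**What to change.** - In 8.4, define the primary efficacy set as all randomised subjects who received at least one dose, grouped as randomised.
- In 3.2.1 and 8.9, count as non-responders all subjects without an evaluable Week 48 histology and PCR result, and those with surgery, ablation or progression before it. State how excision tissue taken before the window is handled, so that Table 4, the excision sentence and the window agree.
- In 8.11.6, exempt the primary endpoint from the no-imputation rule.
- Keep the endpoint-available set as a sensitivity analysis.

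The cost is wording and a slightly lower point estimate. No subjects are added. The critical counts remain 3 and 2, and the stated power holds at the planned 10% missing. Section 8.3 should say whether 20% and 28% are rates among dosed or evaluable subjects, because that decides how much further loss the power can absorb.

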## 8.5 SUBJECT DISPOSITION

Disposition will be summarized by treatment arm for all randomized subjects and will include the number and percentage randomized, the number and percentage who received each dose and the number who completed the trial. The number and percentage of subjects who discontinued will be summarized overall and by reason. The number in each analysis population will also be presented.

## 8.6 DEMOGRAPHIC AND OTHER BASELINE CHARACTERISTICS

Demographic and baseline data will be summarized with descriptive statistics: mean standard deviation, minimum, median, and maximum values for continuous variables, and percentages for categorical variables, by treatment arm, for the mITT population. Prior and concomitant medications will also be summarized with percentages in this fashion.

